9.4.7 Immunogenicity assessments

Samples for the determination of anti-drug antibodies will be collected according to the flowchart in Section 2. All patients will have samples drawn at V1/V1a, but only patients randomised/allocated to concizumab treatment (arms 2, 3 and 4) will have samples drawn at the remaining indicated timepoints in the main part of the trial. In the extension part of the trial, samples must be drawn for all patients (arms 1–4). Sampling should always take place prior to administration of concizumab. In case of suspected hypersensitivity reaction requiring systemic treatment, additional blood samples are to be collected; refer to Section 9.4.8.

Assessment of binding antibodies against concizumab (anti-drug antibodies (ADA) will be performed at specialised laboratories whereas assessment of neutralising antibodies will be performed at Novo Nordisk.

Analysis for ADA will be done with a bridging ECL assay (binding ADA assay) using labelled concizumab for antibody capture and detection. If a sample is confirmed positive in the confirmatory assay, the sample is considered positive for binding antibodies. Confirmed positive

samples will be characterised in a specificity assay for binding to IgG backbone or the S241P mutation. Furthermore, positive samples will be characterised for neutralising activity using a neutralising ADA assay. All antibody assays are validated according to international guidelines and recommendations.

The following data will be available:

- Anti-concizumab antibodies
- Anti-concizumab antibody titres
- Anti-concizumab binding antibodies cross-reacting with IgG4 backbone or S241P mutation
- Anti-concizumab neutralising antibodies

The samples will be analysed and reported to sites at the confirmatory analyses cut-off and at end of extension part (end of trial). A detailed description of the assay methods will be included in the antibody analysis report at the end of the trial.

Patients positive for binding antibodies at end of follow-up may be followed outside this protocol.

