- 5. Major surgery: This intercurrent event is only applicable when a patient is part of the non-interventional study 4322 because planned major surgery is not allowed in trial 4307 after restart. Thus, for a fair comparison this intercurrent event will be handled by use of the 'hypothetical strategy' meaning that the data, from the start of the major surgery and until the stop date when post-surgical period has ended and the patient resumes the regular treatment regimen, will be excluded.

Overall design:

This is a prospective, multicentre, open label clinical trial with two randomised arms and two non-randomised arms. The trial aims to evaluate the effect and safety of daily concizumab prophylaxis administered s.c. in patients with haemophilia without inhibitors. After screening patients will be assigned to randomisation or to allocation into non-randomised treatment arms based on their treatment regimen before the trial. Patients who were randomised to arms 1 and 2 before the pause will enter arm 4 when restarting the trial. Patients who were allocated to arms 3 and 4 before the

Protocol Trial ID: NN7415-4307	CONFIDENTIAL	Date: Version: Status:	25 March 2021 5.0 Final	Novo Nordisk
		Page:	17 of 138	1

pause will re-enter the arm they were initially allocated to. The randomisation into arms 1 and 2 will be restarted with new patients after the treatment pause.

The trial consists of a main part (24 or 32 weeks), an extension part (up to 136 weeks) and a safety follow-up part (7 weeks). The main part of the trial is completed for a patient when the patient has completed 24 weeks of participation (arm 1) or 32 weeks of participation (arms 2,3 and 4). After the main part of the trial, all patients will be offered to continue in the extension part of the trial and receive treatment with concizumab for up to an additional 136 weeks.

Key inclusion criteria:

- Informed consent obtained before any trial-related activities. Trial-related activities are any procedures that are carried out as part of the trial, including activities to determine suitability for the trial.
- Male aged ≥ 12 years at the time of signing informed consent.
- Congenital severe haemophilia A (FVIII <1%) or B (FIX ≤2%).

Key exclusion criteria:

- Known or suspected hypersensitivity to any constituent of the trial product or related products.
 - Known inherited or acquired coagulation disorder other than congenital haemophilia.
 - Presence of confirmed inhibitors ≥ 0.6 BU at screening.

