Treatment arms 2, 3 and 4					•		Mai	in Pa	rt													Е	xtens	ion P	art									Follow- up
Visits (V)	V 1a	V 2a	V 3a	V 4a	V 4a.1	V 5a	V 6a	V 7a	V 8a	V 9a	NA	V 9a.2	NA	V 10a	NA	V 11a	NA	V 12a	NA	V 13a	V 14a	V 15a	V 16a	V 17a	V 18a	V 19a	V 20a	V 21a	V 22a	V 23a	V 24a	V 25a	V 26a	V 27a
Timing of Visit (Weeks)	-3	0ь	1	4	6°	8	12	16	20	24	25	28	30°	32	36	40	44	48	52	56	64	72	80	88	96	104	112	120	128	136	144	152	160	167
Visit Window (Days)	±0	±0	±1	±3	±7°	±3	±3	±3	±3	±3	±1	±3	±7°	±3	±3	±3	±3	±3	±3	±3	±3	±3	±3	±3	±3	±3	±3	±3	±3	±3	±3	±3	±3	±3
Vital signs	X	X	X	X	Xº	X	X	X	X	X	X	X	Xº	X	X	X	X	X	X	X	X	X	X	X	X	X	X	X	X	X	X	X	X	X
Anti- concizumab antibodies ¹	X	Xg		Xg		Xg	Xg	Xg	Xg	X				Xg		X				X			X			X			X				X	X
FVIII/FIX inhibitor analysis	X																																	
Total TFPI		X	X	X		X	X	X	X	X	X	X		X	X	X	X	X	X	X	X	X	X	X	X	X	X	X	X	X	X	X	X	X
OTHER ASSESSMENTS																																		
PRO questionnaires																																		
SF36 V2.0 Health Survey		X		Х		Х		X		X				Xg																				
Patient preference questionnaire										X																								
PROMIS Short Form Upper Extremity		X		X		Х		X		X				Xg																				
PROMIS Numeric		X		X		X		X		X				Xg																				

Protocol	Date:	25 March 2021	Status: Final	Novo Nordisk
Trial ID: NN7415-4307	Version	: 5.0	Page: 23 of 138	

Treatment arm 1					Main	Part	t													Ex	xtensi	on Pa	ırt											Follow- up
Visits (V)	V 1a	V 2a	V 3a ^a	V 4a	NA	V 5a	V 6a	V 7a	V 8a	V 9a	V 9a.1	V 9a.2	V 9a.3	V 10a	V 10a.1	V 11a	V 11a.1	V 12a	V 12a.1	V 13a	V 14a	V 15a	V 16a	V 17a	V 18a	V 19a	V 20a	V 21a	V 22a	V 23a	V 24a	V 25a	V 26a	V 27a
Treatment arms 2, 3 and 4							Mai	in Pa	rt													E	xtens	ion P	art									Follow- up
Visits (V)	V 1a	V 2a	V 3a	V 4a	V 4a.1	V 5a	V 6a	V 7a	V 8a	V 9a	NA	V 9a.2	NA	V 10a	NA	V 11a	NA	V 12a	NA	V 13a	V 14a	V 15a	V 16a	V 17a	V 18a	V 19a	V 20a	V 21a	V 22a	V 23a	V 24a	V 25a	V 26a	V 27a
Timing of Visit (Weeks)	-3	0 _p	1	4	6°	8	12	16	20	24	25	28	30°	32	36	40	44	48	52	56	64	72	80	88	96	104	112	120	128	136	144	152	160	167
Visit Window (Days)	±0	±0	±1	±3	±7°	±3	±3	±3	±3	±3	±1	±3	±7°	±3	±3	±3	±3	±3	±3	±3	±3	±3	±3	±3	±3	±3	±3	±3	±3	±3	±3	±3	±3	±3
Rating Scale - Pain Intensity																																		
Haemophilia Treatment Experience Measure		X								X				Xg																				
Haem-A- QoL ^p	X	Xq		X		X		X		X				Xg																				
PGI-S on physical functioning		X		X		X		X		X				Xg																				

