Footnote a) Phone visit is allowed for patients randomised to arm 1 (on-demand patient) Week 0 is the time of trial restart c) Visit will take place after the concizumab exposure levels are available according to Section 9.2.2 d) Only patients enrolled in the trial after the treatment pause, will sign the Informed Consent at visit 1a e) Only patients enrolled in the trial before the treatment pause, will re-consent at visit 2a Only applicable for patients in arm 1, who are receiving concizumab at visit 9a g) Only applicable for patients in arm 2, 3 and 4, who are receiving concizumab at visit 2a h) Only applicable for patients enrolled in the trial before treatment pause. Site must ensure patients do not violate discontinuation criteria according to Section 8 before reinitiating dosing with concizumab. Patients randomised to arm 1 and 2 before the treatment pause will not be re-randomised at visit 2a Weight only, except at visit 1 where height is measured k) For patients having concizumab dosing at visit 2a there will be a 24-hour PK session at visit 2a and 9a. Please see details for PK sampling in Section 2.1. For on-demand patients (arm 1) only the pre-dose sample will be taken 1) Sample is taken pre-dose. Patients must not inject trial medication on this visit day before the sample is taken. m) Concizumab plasma concentration for dose adjustment (visit 4a for arm 2-4 and visit 9a.2 for arm 1) will be analysed using the concizumab ELISA in vitro diagnostic (IVD) device n) Only one sample to be taken, either factor VIII for HA patients or factor IX for HB patients o) Only applicable for patients having site visit due to dose-escalation Only for patients above ≥17 years old (at visit 1a) q) Only applicable for patients enrolled in the trial before the treatment pause r) Site visit must be performed in case of dose escalation. Phone visit is allowed for patients having dose de-escalation or dose unchanged. See Section 9.2.2 for further details A separate Informed Consent Form must be signed before any samples are taken. See Section 9.7 for further details Whole blood for DNA is only taken at screening

Protocol	Date:	25 March 2021	Status:	Final	Novo Nordisk
Trial ID: NN7415-4307	Version	: 5.0	Page:	26 of 138	

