3.3 Benefit-risk assessment

Concizumab is under development for the prevention of bleeding episodes, including long-term prophylaxis, in patients with haemophilia A and B, regardless of inhibitor status. Until recently, all

CONFIDENTIAL

Date: Version: Status: Page:

25 March 2021 Novo Nordisk Final 29 of 138

5.0

available haemophilia treatment options required frequent intravenous administration of procoagulant compounds. However, a monoclonal antibody therapy emicizumab (Hemlibra®) has now been approved for subcutaneous prophylaxis in HA patients with and without inhibitors. Inhibition of TFPI is a potential new option for the treatment of patients with haemophilia. Concizumab is administered subcutaneously, thus potentially improving convenience compared to clotting factor prophylaxis. Concizumab does not itself involve the risk of inhibitor formation against FVIII or FIX. Therefore, concizumab could represent a major improvement over current treatment options.

As observed for other pro-coagulant compounds, there is a potential risk of thrombosis due to exaggerated pharmacology. Thromboembolic events were observed in toxicity studies in non-human non-haemophiliac primates at high concizumab exposures. In pathological conditions, in which TF is expressed more extensively than considered physiological, e.g. advanced atherosclerosis, cancer, crush injury, or septicaemia, the risk of developing thrombosis and disseminated intravascular coagulation (DIC) may be increased by anti-TFPI treatment. 6.7 Vascular changes observed in the nonclinical toxicity studies were shown to be mediated by disposition of immune complexes (ICs). This is the result of an overwhelmed clearance of ICs, containing concizumab and antibodies against concizumab. Similar changes, if they occur in humans, could lead to organ damage and potentially become life-threatening. It is, however, generally recognised that animal studies are limited in their ability to predict human immune responses to a therapeutic protein.

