5.2.2 On-demand treatment

Patients in arm 1 will continue on-demand treatment with their usual replacement therapy until visit 9a (end of main part). Novo Nordisk will not provide or reimburse on-demand treatment for patients in arm 1. In the extension part, patients in arm 1 will receive daily concizumab subcutaneous injections (see Section 5.2.1).

As noted in Section 5.1, Patients randomised to arm 1 before the pause will go to arm 4 upon restart of the trial. Thus, additional patients will be randomised to arm 1 (and 2) when restarting the trials.

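### Arm 1 has no scheduled on-treatment antibody sample before week 16 on concizumab, against three in arms 2–4, and the flowchart and Section 9.4.7 are inconsistent for arm 1 at visit 10a

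*Protocol*

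**What the plan says.** Protocol Section 9.4.7 contains three statements that matter here.

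- On timing it defers to the visit schedule: "Samples for the determination of anti-drug antibodies will be collected according to the flowchart in Section 2".
- In the main part, after the screening sample, only arms 2, 3 and 4 are sampled.
- For the extension it says "In the extension part of the trial, samples must be drawn for all patients", and names arms 1–4. It also requires every sample to be taken before dosing.

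In the Section 2 flowchart, the row "Anti- concizumab antibodies" applies to all arms at visits 1a, 9a, 11a, 13a and selected later visits. The cells at visits 2a, 4a to 8a and 10a carry footnote g: "Only applicable for patients in arm 2, 3 and 4, who are receiving concizumab at visit 2a". The cells at visits 9a.1, 9a.2, 9a.3 and 10a.1 are blank.

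Section 5.2.2 keeps arm 1 on on-demand treatment until visit 9a, which it treats as the end of that arm's main part. For arms 2–4 the main part runs to week 32, visit 10a (Synopsis; Section 5.1).

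Section 4.3.2.2 lists the number of patients with antibodies to concizumab as a supportive secondary safety endpoint. For arm 1 the window runs from visit 9a to the confirmatory analyses cut-off. Section 5.1 sets that cut-off once arm 1 patients have completed visit 9a, and patients in arms 2 and 4 visit 10a, or have withdrawn. A second antibody endpoint runs to week 167.

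**The concern.** The flowchart follows arm 1's later start for the other blood tests. Coagulation, haematology, biochemistry, concizumab ELISA and free TFPI are all drawn at visits 9a.1, 9a.2, 10a and 10a.1. Antibodies are not, and the protocol gives no reason.

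Three things are at stake.

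- **Detection.** Antibodies that appear and disappear in arm 1 between first dose and week 16 would not be seen at a scheduled visit. In arms 2–4 there are three chances to see them.
- **The endpoint.** Arm 1 is counted from visit 9a, but the cut-off guarantees it no time on drug. A patient with no on-treatment sample could be counted as antibody-negative when he was never tested.
- **Conduct.** A site reading Section 9.4.7 would sample arm 1 at visit 10a. A site reading the flowchart would not.

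The protocol treats immunogenicity as a real safety question. Section 3.3 reports: "Vascular changes observed in the nonclinical toxicity studies were shown to be mediated by disposition of immune complexes". It adds that similar changes, if they occurred in humans, could become life-threatening.

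**Working it through.** There is no planned figure to reproduce, so this is a schedule check. The inputs are the antibody row, the visit weeks and footnote g, all from the Section 2 flowchart. The row has 34 cells, matching the 34 visit columns.

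Weeks on concizumab = trial week − 24 for arm 1 (first dose at visit 9a), and trial week − 0 for arms 2–4 (first dose at visit 2a). Weeks are nominal.

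| Weeks on drug | Arms 2–4 | Arm 1 |
|---|---|---|
| 0 (pre-dose) | V2a: sample | V9a: sample |
| 4 | V4a: sample | V9a.2 (28 − 24): none |
| 8 | V5a: sample | V10a (32 − 24): excluded by footnote g |
| 12 | V6a: sample | V10a.1 (36 − 24): none |
| 16 | V7a: sample | V11a (40 − 24): sample |
| 20 | V8a: sample | V11a.1 (44 − 24): none |
| 24 | V9a: sample | V12a (48 − 24): none |
| 32 | V10a: sample | V13a (56 − 24): sample |

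Counts of scheduled on-treatment samples:

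- Strictly before week 16: arm 1 = 0; arms 2–4 = 3 (weeks 4, 8, 12).
- Through week 16: arm 1 = 1; arms 2–4 = 4.
- Through week 32: arm 1 = 2 (weeks 16, 32); arms 2–4 = 7 (weeks 4, 8, 12, 16, 20, 24, 32).

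**Endpoint window.** Because the cut-off requires only visit 9a in arm 1, time on drug at the cut-off can be close to zero. With the first on-treatment sample at week 16, any arm 1 patient less than 16 weeks past visit 9a has no scheduled on-treatment result. Table 2 plans at least 8 haemophilia A and 12 haemophilia B patients in arm 1, so 8 + 12 = 20 are potentially affected. The actual number depends on enrolment dates, which the documents do not give.

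**Text against flowchart.** Arm 1's main part ends at visit 9a, so visit 10a is in its extension. Section 9.4.7 calls for extension samples in every arm; footnote g removes arm 1. There is a related mismatch at visit 9a: its cell has no footnote and so includes arm 1, although Section 9.4.7 limits post-screening main-part samples to arms 2–4. That sample is arm 1's pre-dose baseline and is needed.

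**The case against.** Several stronger readings are tempting, and the documents do not support them.

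- **That Section 9.4.7 and the flowchart flatly contradict each other.** Section 9.4.7 defers to the flowchart for timing, and its extension sentence says who is sampled without listing visits. From visit 11a on, every antibody cell applies to all arms. The texts can be read together, so this is an inconsistency to reconcile.
- **That arm 1 also lacks the week 16 sample.** It does not: visit 11a is week 16 on drug. The gap is also in scheduled samples only. Sections 9.4.7 and 9.4.8 add antibody samples after certain hypersensitivity reactions in any arm, although these would not find silent antibodies.
- **That an earlier sample would inform arm 1's dose decision.** Under Section 9.4.7, antibody results reach sites only at the confirmatory cut-off and at the end of the extension part. This holds for arms 2–4 too. An early sample would help only in retrospect, and for the same reason it offers no real-time protection.
- **That incidence in arm 1 is understated by a known amount, or that a between-arm comparison is compromised.** The documents give no data on antibody timing or persistence and plan no between-arm antibody test. The 56-week SAP is descriptive, reports by arm, and in its Section 6.2 lists the antibody assessment for arms 2–4 only. The SAP for the confirmatory cut-off is not among the documents.

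It is also fair that Section 3.3 warns that animal studies predict human immune responses poorly, that arm 1 has lighter sampling elsewhere (no 24-hour PK/PD profiles), and that the endpoint running to week 167 gives arm 1 longer follow-up. None of this removes the gap before week 16 or supplies a reason for it.

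**Conclusion.** The point holds as a scheduling gap with a consequence for one supportive safety endpoint. Arm 1 has 0 scheduled on-treatment antibody samples before week 16 on drug, against 3 in arms 2–4, and 2 against 7 through week 32. At the confirmatory cut-off, an arm 1 patient less than 16 weeks past visit 9a contributes no scheduled on-treatment result. Early transient antibodies in arm 1 would be missed, so detection there is weaker than in arms 2–4, by an amount that cannot be derived from the documents.

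The bleeding analyses are not affected. The conclusion rests on the flowchart as printed, on nominal visit weeks, and on the visit 9a sample in arm 1 being taken before the first dose, as Section 9.4.7 requires. It is worth correcting because the remedy needs no new visits.

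**What to change.** **Sampling.** In the flowchart's antibody row, remove footnote g at visit 10a and add arm 1 samples at visits 9a.2 and 10a.1. Arm 1 is then sampled at weeks 4, 8, 12 and 16. The visit 9a.2 cell should be marked as arm 1 only, because arms 2–4 also attend that visit; visit 10a.1 exists only for arm 1. Adding visits 11a.1 and 12a (weeks 20 and 24, the latter also marked arm 1 only) is optional and would give 7 samples through week 32, as in arms 2–4.

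**Text.** Amend Section 9.4.7 to agree with the flowchart at visit 10a, and to state that arm 1's visit 9a sample is its pre-dose baseline.

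**Endpoint.** Count in the denominator only patients with at least one post-baseline antibody sample, and present arm 1 separately from arms 2–4. This is needed even with the added samples: they shorten the window without a result from under 16 weeks to under 4, but do not close it. These reporting rules can be adopted whatever has already been sampled.

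**Cost.** 3 visits × about 20 patients = about 60 assays; with the two optional visits, 5 × 20 = about 100. Pre-dose blood is already drawn from arm 1 at all of these visits. The burden is not negligible for light adolescents. Table 20 caps a single draw at 20.0–23.2 mL for 25–29 kg, and Section 9 cites an average of 28 mL per site visit for patients enrolled before the pause. Table 21 ranks immunology fifth, ahead of free TFPI and thrombin generation, so an extra tube could displace those measurements in these patients.

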9.4.8 Hypersensitivity reaction

If suspicion of a hypersensitivity reaction occurs, patients should be instructed to contact the site staff as soon as possible for further guidance, see Appendix 5.

In the event of a severe local and/or systemic hypersensitivity reaction possibly or probably related to trial product, blood sampling for assessment of anti-concizumab IgE antibodies as well as anti-concizumab antibodies should be conducted in relation to the reaction and no later than 1-2 weeks after the event. Additional testing may be performed locally if deemed relevant (e.g. anti-Host Cell Proteins (HCP) antibodies).

In the event of a severe systemic hypersensitivity reaction to trial product, it is recommended also to test for tryptase (total and/or mature tryptase) within 3 hours of the reaction. Moreover, a baseline tryptase measurement is necessary 1-2 weeks after the immediate severe hypersensitivity reaction due to individual variation in tryptase baseline concentration.

A follow up visit should be conducted 3-4 weeks post the allergic reaction with repeated blood sampling for assessment of anti-concizumab IgE antibodies as well as anti-concizumab antibodies and if possible also at a visit 3 month after the hypersensitivity reaction for assessing the persistence of the IgE response. Tryptase measurements are not required at the follow up visits.

Additionally, basophil activation testing may be performed if deemed relevant. This can be performed using existing samples and/or by analysing the patient's basophil cells from an additional blood sample taken 3-4 weeks and no later than 2 months after the event. Similarly, prick tests and/or intra-dermal tests may be performed if relevant using trial product or components of trial product. Complement may be measured in case of suspicion of immune complex mediated hypersensitivity reactions.

The following additional tests can be performed locally or at special laboratories if deemed relevant:

• Anti-concizumab IgE antibodies

Status:

Page:

Final

80 of 138

Anti-concizumab antibodies (additional to scheduled time points)

- Anti-Host Cell Proteins (HCP) antibodies
- Anti-HCP IgE antibodies
- Basophil activation results
- Prick test/intra-dermal test
- Complement test results
- Tryptase (total and/or mature tryptase)

In case laboratory samples for severe hypersensitivity reactions are analysed at special laboratories, the results from the analysis will be reported directly to site(s) via Novo Nordisk.

Hypersensitivity reactions including test results should be reported as an AE requiring additional data collection, see Section 9.3.1

9.4.9 Injection site reactions

Injection site reactions must be recorded on the AE form and the injection site reaction form. Signs and symptoms of injection site reactions include but are not limited to pain, numbness, itching, burning, redness, induration, swelling, dimpling, macula, haematoma and bleeding.

9.5 Pharmacokinetics

Concizumab will be quantified using a validated ELISA assay. Recombinant human TFPI will be used to capture concizumab. A colorimetric detection signal is obtained by the enzymatic reaction of horseradish peroxidase labelled anti-human IgG4 specific antibodies with the chromogenic substrate TMB (3,3′,5,5′-tetramethylbenzidine). The amount of anti-TFPI present in the calibration, quality control and test samples correlate with the obtained signal strength.

Validation of the assay follows current guidelines for bioanalytical method validation. Bioanalytical data will be reported in a bioanalytical report.

The concizumab ELISA will be used to evaluate exposure and pharmacokinetics of concizumab.

For patients dosed with concizumab from visit 2a (patients in arms 2, 3 and 4), two 24-hour PK/PD-sessions will be conducted at visits 2a and 9a. The concizumab dose will be administered in the abdomen and blood samples will be drawn pre-dosing, 3, 6, 9 and 24 hours after dosing. Care must be taken to ensure the 24-hour sample is drawn before the next daily dose of concizumab is administered. At the day of visit 9a patients should not dose themselves at home; the dose will be administered at site followed by blood sampling. The dose should be taken at site in the abdomen and care must be taken to ensure the 24-hour sample is drawn before the next daily dose of concizumab is given.

For patients who had a 24-hour PK profile measured at visit 2 prior to the treatment pause, a new 24-hour PK profile at visit 2a should not be conducted after restart of the trial. For these patients, only pre-dose and 24-hour post-dose samples should be taken at visit 2a. Care must be taken to ensure the 24-hour sample is drawn before the next daily dose of concizumab is administered.

Status:

Page:

81 of 138

Following items must be recorded in the eCRF:

- Time of lab samples taken
- Time of concizumab dose
- Injection site location

See Section 2.1 for the specific timepoints for the PK analysis.

In addition to the two PK/PD sessions, pre-dose concizumab levels (C_{trough}) will be measured throughout the concizumab treatment period. These blood samples must be drawn prior to trial product administration as specified in the flowchart in Section 2. If the patient has taken the daily dose of concizumab before collection of the concizumab ELISA sample, then visit 4a (arm 2, 3, 4) or visit 9a.2 (arm 1) should be rescheduled.

9.6 **Pharmacodynamics**

Pharmacodynamics assessments Thrombin Generation, and Free TFPI are described in Section 9.2.7. For patients dosed with concizumab from visit 2a (patients in arms 2, 3 and 4), two 24-hour PK/PD-sessions will be conducted at visits 2a and 9a; see Section 9.5 for further details.

9.7 **Human Biological Specimen for storage**

